4.5 Treatments

4.5.1 Treatments To Be Administered

This study is designed with two blinded treatment groups (C1INH vs. Placebo). Each group will include 35 patients in a treatment arm and 35 patients in a placebo arm.

This design is statistically powered to show significant differences if there is a 30--50% reduction in the treatment group and may trend towards positive treatment effect since extensive DGF (40--50%) is expected in ECD and DCD recipients. The dose of C1INH chosen is (50U/kg) (round to the nearest 500unit) X2 (high-dose treatment) which should increase serum C1INH levels significantly above physiologic levels. This is based on our observations from our experience using C1INH vs. placebo to prevent antibody-mediated rejection in humans. In those randomized to placebo, an equivalent volume of placebo (0.9%) normal saline) will be administered prior to graft reperfusion.

Patients who fulfill all I/E criteria will be enrolled into this Phase I/II study.

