4.5.7 Selection And Timing Of Dose For Each Subject

The active treatment arm (Berinert® 50U/kg, maximum dose 4000U) will be compared to a placebo control treatment arm, with a total of 35 adult subjects in each study group. A total of 70 adult subjects will be enrolled in the study and additional subjects will not be enrolled to replace dropouts. This design is statistically powered to show differences in DGF with a 30-50% reduction in DGF predicted for the Berinert® study group. Treatment effect will be investigated following intravenous treatment with two doses of Berinert® or an equivalent volume of placebo (0.9% normal saline) pre-operatively prior to graft reperfusion and repeated 24 hours post-transplantation.

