5.5 Confidentiality

All records identifying the subject will be kept confidential and, to the extent permitted by the applicable laws and/or regulations, will not be made publicly available.

Subject names will not be supplied to the sponsor. Only the subject number and subject initials will be recorded in the case report form, and if the subject name appears on any other document (e.g., pathologist report), it must be obliterated before a copy of the document is supplied to the sponsor. Study findings stored on a computer will be stored in accordance with local data protection laws. The subjects will be informed in writing that representatives of the sponsor, EC/IRB, or Regulatory Authorities may inspect their medical records to verify the information collected, and that all personal information made available for inspection will be handled in strictest confidence and in accordance with local data protection laws.

If the results of the study are published, the subject's identity will remain confidential.

The investigator will maintain a list to enable subjects' records to be identified.

- 6 Statistical Methods And Determination Of Sample Size
- 6.1 Statistical And Analytical Plans
- 6.2 Determination of Sample Size

The sample size calculations were based on a conservative assessment aimed to show $\sim 50\%$ reduction in DGF rates with C1INH application. Data from the Cedars-Sinai Medical Center Renal Transplant Program for DGF rates are shown below:

CONFIDENTIAL

	Transplants 7/1/2011 until 7/1/2013
	N=237
	DGF Rate
ECD	27/36 (75%)
DCD	9/13 (69%)
Final Cr >/=1.5	28/37 (76%)
Non-ECD/DCD/Cr<1.5	33/100 (33%)

Briefly, the DGF rates at our center for the proposed study groups are >70% compared to 33% for SCD donors. Thus, a conservative proposal is explored below. The sample size calculations showing 35 subjects per group would sufficiently power the study (80%) to show 50% reduction when an anticipated DGF rate of 50% for the study group is anticipated.

The "proportion" below is the proportion with DGF. A 2-sided test (to be more conservative) was performed. We assumed a 50% DGF rate in the Placebo group. Treated group DGF rate vary: 20%, 25%, and 30%. sample size per group for 80% and 90% power are shown.

Two group continuity corrected χ^2 test of equal proportions (odds ratio = 1) (equal n's)

-	1	2	3	4	5	6
Test significance level, \Box	0.050	0.050	0.050	0.050	0.050	0.050
1 or 2 sided test?	2	2	2	2	2	2

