Treated Group	0.200	0.250	0.300	0.200	0.250	0.300
proportion, π_1 Placebo Group	0.500	0.500	0.500	0.500	0.500	0.500
proportion, π_2 Odds ratio,						
$\psi = \pi_2 (1 - \pi_1) / [\pi_1 (1 -$	4.000	3.000	2.333	4.000	3.000	2.333
π_2)]						
Power (%)	80	80	80	90	90	90
n per group	45	66	103	58	85	134

A two group continuity corrected χ^2 test with a 0.05 two-sided significance level will have 80% power to detect the difference between a Treated Group proportion, π_1 , of 0.20 and a Placebo Group proportion, π_2 , of 0.50 (odds ratio of 4.00) when the sample size in each group is 45.

Two group continuity corrected χ^2 test of equal proportions (odds

Note: The odds ratio (OR) is the OR for DGF. In Column 1, OR = 4, so the odds of DGF in the Placebo group is 4 times the odds of DGF in the Treated group.

One-sided tests:

proportion, π_1

 π_2)

ratio = 1) (equal n's)						
	1	2	3	4	5	6
Test significance level, \Box	0.050	0.050	0.050	0.050	0.050	0.050
1 or 2 sided test?	1	1	1	1	1	1
Treated Group	0.200	0.250	0.300	0.200	0.250	0.300

Placebo Group	0.500	0.500	0.500	0.500	0.500	0.500
proportion, π_2 Odds ratio,						
$\psi = \pi_2 (1 - \pi_1) / [\pi_1 (1 -$	4.000	3.000	2.333	4.000	3.000	2.333

 Power (%)
 80
 80
 80
 90
 90
 90

 n per group
 37
 54
 83
 48
 71
 111

Statistical Assumptions

- Since this study is a Phase I/II, we will primarily explore the safety of the proposed dose in the renal transplant population receiving high-risk ECD and DCD kidneys. Our previous experience in a population of highly-HLA sensitized renal allograft recipients showed that administration of 20U/kg (8 doses in 1 month) was safe and without AE or SAE when compared to placebo (NCT01134510). Based on the calculations above, we propose a randomized, placebo controlled trial of C1INH vs. placebo entering 35 eligible patients into both arms of the study.
- 7 Adverse Events (AEs)
- 7.1 Adverse Event (AE) Monitoring
- 7.2 Adverse Event (AE) Definitions
- 7.2.1 Adverse Events (AEs)

An AE is any untoward medical occurrence in a subject or clinical investigation subject administered with a pharmaceutical product. The AE does not necessarily have to have a causal relationship with this treatment. An AE can therefore

be any unfavorable and unintended sign (including an abnormal laboratory finding), symptom, or disease temporally associated with the use of an investigational product, whether or not considered related to the medicinal product.

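### With 35 per arm the trial has about 50% power, not 80%, to detect a halving of a 50% DGF rate; the protocol's own table asks for 66 per arm

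*Combined protocol and SAP*

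**What the plan says.** Section 6.2 (Determination of Sample Size) states that "35 subjects per group would sufficiently power the study (80%) to show 50% reduction when an anticipated DGF rate of 50" per cent is expected. The inputs are given beside it: "We assumed a 50% DGF rate in the Placebo group" and "A 2-sided test (to be more conservative) was performed". Treated-group rates of 20%, 25% and 30% are then tabulated for a continuity-corrected chi-square test. The sentence under the two-sided table takes its most favourable column, 20% against 50%: the "test with a 0.05 two-sided significance level will have 80% power to detect the difference" "when the sample size in each group is 45". A one-sided table follows. Section 6.2 closes by proposing 35 patients per arm on the strength of these calculations.

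The claim is repeated more broadly elsewhere. Section 4.5.1: "This design is statistically powered to show significant differences if there is a 30--50% reduction in the treatment group". Section 4.5.7: "This design is statistically powered to show differences in DGF with a 30-50% reduction in DGF predicted for the Berinert® study group". Section 4.5.7 also says that "additional subjects will not be enrolled to replace dropouts", and nothing in 6.2 allows for loss.

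**The concern.** A 50% reduction from a 50% rate is 50% against 25%, which is the second column of each table in 6.2. That column reads 66 per group two-sided and 54 one-sided at 80% power, not 35. The smallest entry anywhere is 37, for a one-sided test of a 60% reduction. The lower end of the range in 4.5.1 and 4.5.7, a 30% reduction, is in no column. The tables stop at a 40% reduction, which already needs 103 per group two-sided.

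Section 4.6.1.1 lists dialysis in the first 7 days among the primary efficacy endpoints, and Section 2.1 makes the choice of dose and endpoint for Phase III a secondary objective. If the placebo rate is the assumed 50%, a treatment that truly halves DGF would fail to reach significance about half the time. Readers told that power was 80% could take that result as evidence against the drug.

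**Working it through.** **Inputs (Section 6.2).** Placebo rate p₂ = 0.50; treated rate p₁ = 0.20, 0.25 or 0.30; alpha 0.05; continuity-corrected chi-square; equal groups. For the 30% reduction in 4.5.1 and 4.5.7, p₁ = 0.50 × 0.70 = 0.35. Those sections pair no placebo rate with the range in so many words, so the 50% of Section 6.2 is assumed.

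**Step 1: reproduce the tables.** With d = p₂ − p₁ and p̄ = (p₁ + p₂)/2:

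- n₀ = [z_α √(2p̄(1−p̄)) + z_β √(p₁(1−p₁) + p₂(1−p₂))]² / d²
- n = (n₀/4) [1 + √(1 + 4/(n₀d))]²

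For 0.25 against 0.50, two-sided, 80% power: n₀ = (1.960 × 0.6847 + 0.8416 × 0.6614)² / 0.0625 = 57.7, and n = 65.4, rounded up to 66. The same formulas return every entry:

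| Treated vs placebo | 2-sided 80% | 2-sided 90% | 1-sided 80% | 1-sided 90% |
|---|---|---|---|---|
| 20% vs 50% | 45 | 58 | 37 | 48 |
| 25% vs 50% | 66 | 85 | 54 | 71 |
| 30% vs 50% | 103 | 134 | 83 | 111 |

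The tables are therefore sound, and the error lies in the sentence about 35 per group.

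**Step 2: power at 35 per arm.** Inverting the correction gives n₀ = n(1 − 1/(nd))², and power is Φ{[d√n₀ − z_α √(2p̄(1−p̄))] / √(p₁(1−p₁) + p₂(1−p₂))}.

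- 25% vs 50%: n₀ = 35 × (1 − 1/8.75)² = 27.46; power = Φ[(0.25 × 5.240 − 1.960 × 0.6847)/0.6614] = Φ(−0.048) = 48.1%.
- 35% vs 50%: n₀ = 35 × (1 − 1/5.25)² = 22.94; power = Φ[(0.15 × 4.789 − 1.960 × 0.6991)/0.6910] = Φ(−0.943) = 17.3%.

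**Step 3: does another test rescue the claim?** Each cell gives the formula result, with exact binomial enumeration in brackets.

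| Test at n = 35 per arm | 25% vs 50% | 35% vs 50% |
|---|---|---|
| Two-sided, corrected (as planned) | 48.1% (49.8%) | 17.3% (17.0%) |
| Two-sided, uncorrected | 58.2% (59.0%) | 24.2% (23.4%) |
| One-sided, corrected | 61.0% (63.0%) | 26.6% (29.3%) |
| One-sided, uncorrected | 70.3% (72.0%) | 35.2% (38.2%) |

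None reaches 80%. Under the planned test, 80% power at 35 per arm requires a treated rate of about 16%, a relative reduction of about 67%. For 35% against 50%, 80% power would need about 183 per arm.

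**Step 4: sensitivity to the placebo rate** (two-sided, corrected, 35 per arm).

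| Placebo rate | 50% reduction | 30% reduction |
|---|---|---|
| 40% | 34% | 12% |
| 50% | 48% | 17% |
| 60% | 63% | 24% |
| 70% | 78% | 34% |
| 72% | 81% | 36% |
| 75% | 85% | 40% |

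**Step 5: losses.** The protocol gives no dropout rate. If, for illustration, 32 per arm were evaluable, power for 25% against 50% would fall to 44%.

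**The case against.** The strongest reply is that 50% was chosen as a cautious figure. The centre's own data in Section 6.2 show DGF of 75% (27/36) for ECD, 69% (9/13) for DCD and 76% (28/37) where final creatinine was at least 1.5. At such rates, 35 per arm does give roughly 78–85% power for a halving. That is true, and it makes the consequence conditional on the placebo rate. It does not save the statement, because the sentence and every column use 50%. Section 4.5.1 expects only 40–50% in ECD and DCD recipients, and Section 4.2.1 also admits other kidneys with a risk index of 3–8. Nor does it help the 30% end of the range, where power is at most about 40% even at a 75% placebo rate.

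A second reply is that this is a Phase I/II study whose primary objective is safety. That is a fair reason to accept 70 patients, but it does not make a wrong power figure right.

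A third is that Section 6.1 carries no text and the synopsis promises only descriptive and comparative statistics, so the analysis test is not fixed. Uncorrected, two-sided power for a halving is 58–59% rather than 48–50%, which is still far short of 80%. Finally, the lack of a dropout allowance is a minor point here, since an endpoint measured in the first 7 days should lose few patients.

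**Conclusion.** The concern holds. Under the protocol's own assumptions (50% placebo rate, two-sided 0.05, continuity correction, all 35 per arm evaluable), power for a 50% reduction is 48–50%, about 30 points below the stated 80%. The protocol's table requires 66 per arm, 132 in all, nearly twice the planned number. Power for a 30% relative reduction is about 17%, so the range claimed in 4.5.1 and 4.5.7 is unsupported throughout. Dropping the correction or testing one-sided changes the figures but not the conclusion. Only a placebo rate of about 70% or more would bring a halving to around 80%, and the plan does not assume that rate. This must be corrected, because the plan attributes to the trial a property it does not have.

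**What to change.** In 6.2, 4.5.1 and 4.5.7, replace the power claims with a statement along these lines: with 35 per arm, a two-sided 0.05 continuity-corrected test and a 50% placebo rate, power is about 50% for 50% against 25%, about 17% for 50% against 35%, and 80% only for 50% against about 16%. Amend the closing sentence of 6.2 as well, since the calculations above it do not yield 35; give the actual reason for the number, such as the safety aim.

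Add that DGF will be reported as a risk difference with a 95% confidence interval, and that a non-significant result is not evidence of no effect. The expected half-width at 50% against 25% is 1.96 × √[(0.25 + 0.1875)/35] = 0.219, or about 22 percentage points.

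The cost is protocol wording and a less favourable power figure; no extra patients are needed. If the sponsor wants to keep an 80% claim instead, it must either enrol 66 per arm or justify a placebo rate near 72% for the population actually eligible, and reconcile that with the 40–50% in 4.5.1.

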7.2.2 Serious Adverse Event (SAE)

An SAE is any untoward medical occurrence that at any dose:

- results in death
- is life-threatening
- requires in-patient hospitalization or prolongation of existing hospitalization
- results in persistent or significant disability or incapacity
- is a congenital anomaly or birth defect
- is an important medical event

Life-threatening: The term "life-threatening" in the definition of "serious" refers to an adverse event in which the subject was at risk of death at the time of the event. It does not refer to an adverse event which hypothetically might have caused death if it were more severe.

Hospitalization: Any AE leading to hospitalization or prolongation of hospitalization will be considered as Serious, UNLESS at least one of the following exceptions are met :

 The admission is pre-planned (i.e., elective or scheduled surgery arranged prior to the start of the study)

OR

• The admission is not associated with an adverse event (e.g., social hospitalization for purposes of respite care)

However it should be noted that invasive treatment during any hospitalization may fulfill the criterion of 'medically important' and as such may be reportable as an SAE dependent on clinical judgment. In addition where local regulatory authorities specifically require a more stringent definition, the local regulation takes precedent.

Disability: a substantial disruption of a person's ability to conduct normal life's functions.

Important medical event: Any adverse event may be considered serious because it may jeopardize the subject and may require intervention to prevent another serious condition. As guidance for determination of important medical events refer to the "WHO Adverse Reaction Terminology - Critical Terms List". These terms either refer to or might be indicative of a serious disease state.

Such reported events warrant special attention because of their possible association with a serious disease state and may lead to more decisive action than reports on other terms.

SAE medwatch reports WILL NOT be filled out for any prolonged hospital admissions or readmissions that are related to expected complications of the patients' primary disease (ESRD). For example, prolonged admissions for dialysis or readmission for fluid overload as a consequence of ESRD since this this is an expected complication of the patients' disease state and not related to study drug. These events will be adjudicated by the PI. Otherwise, all SAEs medwatch reports will be submitted to the IRB, study sponsor and FDA.

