1.1.1.6 Primary Safety Endpoints

• Overall incidence of adverse events and serious adverse events and relationship to the study treatment including but not limited to, occurrence of infections, thrombosis of the allograft, vascular thromboses, bleeding, death, vital signs, and abnormal lab values.

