Adverse events associated with the use of a drug in humans, whether or not considered drug related, include the following:

- An AE occurring in the course of the use of a drug product in professional practice,
- An AE occurring from an overdose whether accidental or intentional,
- An AE occurring from drug abuse,
- An AE occurring from drug withdrawal.
- An AE where there is a reasonable possibility that the event occurred purely as a result of the subjects participation in the study (e.g. adverse event or serious adverse event due to discontinuation of antihypertensive drugs during wash-out phase) must also be reported as an adverse event even if it is not related to the investigational product.

The clinical manifestation of any failure of expected pharmacological action is not recorded as an AE if it is already reflected as a data point captured in the CRF. If, however, the event fulfills any of the criteria for a "serious" AE (SAE), it must be recorded and reported as such.

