7.2.4 Relationship Of Adverse Event To Investigational Product

The assessment of the relationship of an AE to the administration of study drug is a clinical decision based on all available information at the time of the completion of the case report form.

An assessment of 'No' would include:

- 1. The existence of a clear alternative explanation, e.g., mechanical bleeding at surgical site; or
- 2. Non-plausibility, e.g., the subject is struck by an automobile when there is no indication that the drug caused disorientation that may have caused the event; cancer developing a few days after the first drug administration.

An assessment of 'Yes' indicates that there is a reasonable suspicion that the adverse event is associated with the use of the investigational drug.

Factors to be considered in assessing the relationship of the adverse event to study drug include:

- The temporal sequence from drug administration: The event should occur after the drug is given. The length of time from drug exposure to event should be evaluated in the clinical context of the event
- Recovery on discontinuation (de-challenge), recurrence on reintroduction (re-challenge): Subject's response after drug discontinuation (de-challenge) or subjects response after drug re-introduction (re-challenge) should be considered in the view of the usual clinical course of the event in question
- Underlying, concomitant, intercurrent diseases: Each report should be evaluated in the context of the natural history and course of the disease being treated and any other disease the subject may have

CONFIDENTIAL

- Concomitant medication or treatment: The other drugs the subject is taking or the treatment the subject receives should be examined to determine whether any of them may be suspected to cause the event in question
- The pharmacology and pharmacokinetics of the test drug: The pharmacokinetic properties (absorption, distribution, metabolism and excretion) of the test drug(s), coupled with the individual subject's pharmacodynamics should be considered.

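### Section 7.2.2 labels ESRD-attributed dialysis and fluid-overload admissions unrelated to study drug in advance, in conflict with the case-by-case causality assessment in 7.2.4

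*Combined protocol and SAP*

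**What the plan says.** The last paragraph of section 7.2.2 rules out a MedWatch form for certain hospital stays attributed to ESRD, which it names as the primary disease. No such form is to "be filled out for any prolonged hospital admissions or readmissions that are related to expected complications". The examples are "prolonged admissions for dialysis or readmission for fluid overload as a consequence of ESRD". The reason given is that this is an expected complication of the "disease state and not related to study drug". The next sentence reads "These events will be adjudicated by the PI". It does not say whether the PI rules on the exemption, on seriousness or on causality, or by what criteria. MedWatch reports for all other SAEs go to the IRB, sponsor and FDA.

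Other sections bear on the same events:

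- **7.2.1** allows a failure of the drug's expected action to go unrecorded as an AE when the CRF already captures it as data. If the event meets a seriousness criterion, however, "it must be recorded and reported as such".
- **7.2.2**, in its definition, makes prolonged hospitalization a seriousness criterion. It lists two exceptions: a pre-planned admission, and an admission not associated with an adverse event.
- **7.2.4** states: "The assessment of the relationship of an AE to the administration of study drug is a clinical decision based on all available information".
- **1.1.1.6 Primary Safety Endpoints** reads: "Overall incidence of adverse events and serious adverse events and relationship to the study treatment".
- **4.6.2.5** includes a halt trigger for AEs attributable to C1 inhibitor.
- **7.3** requires SAE reports within 24 hours, with no ESRD exception. It requires reporting to the manufacturer of events believed or possibly attributable to the product.

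**The concern.** Every patient in this trial has just received a kidney. Dialysis in the first week is the conventional definition of DGF that the Introduction adopts, and it is part of the primary efficacy endpoint in 4.6.1.1. The synopsis rationale itself links DGF to longer hospital stays. A prolonged stay for dialysis can therefore be the very outcome that C1INH is given to change, described as a complication of ESRD. If the drug harmed the graft, the harm could look the same.

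Whether such an event belongs to ESRD, to the graft or to the drug is the causality question. The protocol answers it by rule. What is at stake is the relatedness tabulation within the primary safety endpoint, in a study whose stated primary objective is safety. The halt trigger and the manufacturer reporting that depend on attribution are also affected.

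**Working it through.** The point rests on no figure in the plan, so the check is a comparison of sections followed by a rough scale.

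**1. Causality.** Section 7.2.4 requires a judgement on all available information and lists factors such as timing, pharmacology and concurrent disease. The closing paragraph of 7.2.2 supplies the answer in advance for a class of events. Both cannot govern the same event. The adjudication sentence does not settle this, because it does not say that the PI may overturn the label.

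**2. Seriousness and recording.** Dialysis is captured in the CRF as endpoint data, so an admission prolonged by dialysis is the case that 7.2.1 has in view: a possible failure of drug action that is serious and must still be reported as an SAE. ESRD complications are not among the two hospitalization exceptions in 7.2.2. If the exemption covers MedWatch forms only, a site can follow 7.2.1, 7.2.2 and 7.3 together. If it is read as covering SAE status, it cannot. The text does not say which is meant.

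**3. What depends on attribution.**
- The relationship part of the primary safety endpoint: an event labelled unrelated by rule lowers the count of related events.
- The halt trigger in 4.6.2.5 for AEs attributable to C1 inhibitor.
- The manufacturer reporting in 7.3 for possibly attributable events.

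The label applies alike to both arms, but the number of events it covers need not be equal. If C1INH changes DGF in either direction, the arms will have different numbers of relabelled events.

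**4. What does not depend on it.**
- CRF recording of all AEs (7.2.6) and 24-hour SAE reporting (7.3).
- DSMB safety review and the quarterly AE and SAE assessment (section 3).
- The separate trigger in 4.6.2.5 for allograft thrombosis and thromboembolic events, which needs no attribution.
- Dialysis use at days 14, 28, 60 and 90 as a secondary endpoint (4.6.1.2).

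The efficacy endpoints are only a partial substitute. The primary dialysis endpoints exclude patients dialysed for hyperkalemia (4.6.1.1), dialysis duration is defined by sessions in the first 7 days (4.6.4.12), and readmission and fluid overload are not endpoints.

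**5. Scale of the overlapping group.** Inputs are 35 patients per arm and the DGF rates in section 6.2: 50% on placebo for planning, halved on treatment, and above 70% for the centre's study groups, taken here as 70%. Expected DGF patients = 35 × (placebo rate + treated rate).

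| Assumption | Calculation | Of 70 |
|---|---|---|
| 50% placebo, halved | 35 × (0.50 + 0.25) | 26.25 |
| 50%, no effect | 35 × (0.50 + 0.50) | 35 |
| 70% placebo, halved | 35 × (0.70 + 0.35) | 36.75 |
| 70%, no effect | 35 × (0.70 + 0.70) | 49 |

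The range is 26.25/70 = 37.5% to 49/70 = 70%. These are DGF patients, not exempted admissions. Not every DGF patient will have a prolonged stay or readmission, and a patient without DGF can be readmitted for fluid overload.

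**The case against.** The strongest defence is that the paragraph withholds one form and nothing else. It does not say that the events are not SAEs, and the channels in step 4 stay open. A blinded PI (4.5.3) adjudicates. Section 7.2.4 itself accepts a clear alternative explanation as grounds for an assessment of no relationship, and ESRD could be one. The exemption is also confined to events attributed to ESRD.

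Much of this stands, and it rules out several stronger readings that a reader might infer:

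- *That these events drop out of serious-event oversight.* They do not; recording, 24-hour reporting and periodic review remain.
- *That causality is settled before anyone looks.* The PI looks, though alone and without a stated question or criteria.
- *That a renal harm of the drug could not appear.* Dialysis, creatinine and graft survival are followed to day 90.
- *That graft thrombosis would be hidden.* It is named in the primary safety endpoint and is a halt trigger whatever its attribution.

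What does not stand is the appeal to an alternative explanation. Section 7.2.4 lets the assessor reach that conclusion for a given case; 7.2.2 assumes it for the class. Confinement to ESRD does not help either, since attributing a post-transplant dialysis stay to ESRD rather than to the graft or the drug is the judgement in dispute.

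**Conclusion.** The concern holds as a conflict between rules. The advance label of non-relatedness in 7.2.2 contradicts 7.2.4 and sits badly with 7.2.1 and with the hospitalization exceptions in 7.2.2. It can bias the relatedness component of the primary safety endpoint and weaken the attribution-based halt trigger. It does not remove the events from oversight.

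The size cannot be stated as a number of events, because the documents give no rate of prolonged stays or readmissions. The table in step 5 should not be read as saying that a third or more of patients will have exempted admissions; it shows only that the overlapping group is large under the protocol's own rates.

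The conclusion assumes that sites would apply the label as written when they complete the relationship field. The body of the protocol does not say whether the DSMB sees these admissions by arm. The charter cited as Appendix E is not in the text reviewed and may say so. The change should be made, but the point does not invalidate the design.

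**What to change.** Amend the wording as follows:

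1. In 7.2.2, delete the words that declare these events unrelated to study drug, and assess each one under 7.2.4.
2. State that the exemption covers MedWatch submission only, and that each such admission is still recorded under 7.2.6 and reported as an SAE under 7.3.
3. State what the PI adjudicates and by what criteria.
4. Add a table of these admissions by arm to the existing quarterly safety review, for the DSMB only. Someone outside the blinded team should prepare it, since 4.5.3 keeps investigators and sponsor blinded.
5. Reconcile 7.2.1, both parts of 7.2.2, 7.2.4 and 7.3 on this basis.

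The cost is a protocol amendment, more SAE forms and one extra table. The MedWatch exemption is kept, so these events add no routine MedWatch submissions. If the DSMB charter already provides for such a table, item 4 needs only a cross-reference.
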